8.3.4. Regulatory Reporting Requirements for SAEs

Prompt notification by the investigator to the sponsor of an SAE is essential so that legal obligations and ethical responsibilities toward the safety of participants and the safety of a study intervention under clinical investigation are met.

The sponsor has a legal responsibility to notify both the local regulatory authority and other regulatory agencies about the safety of a study intervention under clinical investigation. The sponsor will comply with country-specific regulatory requirements relating to safety reporting to the regulatory authority, IRBs/ECs, and investigators.

Investigator safety reports must be prepared for SUSARs according to local regulatory requirements and sponsor policy and forwarded to investigators as necessary.

An investigator who receives SUSARs or other specific safety information (eg, summary or listing of SAEs) from the sponsor will review and then file it along with the SRSD(s) for the study and will notify the IRB/EC, if appropriate according to local requirements.

8.3.5. Exposure During Pregnancy or Breastfeeding, and Occupational Exposure

Environmental exposure, occurs when a person not enrolled in the study as a participant receives unplanned direct contact with or exposure to the study intervention. Such exposure may or may not lead to the occurrence of an AE or SAE. Persons at risk for environmental exposure include healthcare providers, family members, and others who may be exposed. An environmental exposure may include exposure during pregnancy, exposure during breastfeeding, and occupational exposure.

Any such exposure to the study intervention under study are reportable to Pfizer Safety within 24 hours of investigator awareness.

8.3.5.1. Exposure During Pregnancy

An EDP occurs if:

- A female participant is found to be pregnant while receiving or after discontinuing study intervention.
- A female is found to be pregnant while being exposed or having been exposed to study intervention due to environmental exposure. Below are examples of environmental EDP:
 - A female family member or healthcare provider reports that she is pregnant after having been exposed to the study intervention by ingestion.

The investigator must report EDP to Pfizer Safety within 24 hours of the investigator's awareness, irrespective of whether an SAE has occurred. The initial information submitted should include the anticipated date of delivery (see below for information related to termination of pregnancy).

- If EDP occurs in a participant or a participant's partner, the investigator must report this information to Pfizer Safety on the CT SAE Report Form and an EDP Supplemental Form, regardless of whether an SAE has occurred. Details of the pregnancy will be collected after the start of study intervention and until after the start of study interventions and until a minimum of 28 calendar days after last dose.
- If EDP occurs in the setting of environmental exposure, the investigator must report information to Pfizer Safety using the CT SAE Report Form and EDP Supplemental Form. Since the exposure information does not pertain to the participant enrolled in the study, the information is not recorded on a CRF; however, a copy of the completed CT SAE Report Form is maintained in the investigator site file.

Follow-up is conducted to obtain general information on the pregnancy and its outcome for all EDP reports with an unknown outcome. The investigator will follow the pregnancy until completion (or until pregnancy termination) and notify Pfizer Safety of the outcome as a follow-up to the initial EDP Supplemental Form. In the case of a live birth, the structural integrity of the neonate can be assessed at the time of birth. In the event of a termination, the reason(s) for termination should be specified and, if clinically possible, the structural integrity of the terminated fetus should be assessed by gross visual inspection (unless preprocedure test findings are conclusive for a congenital anomaly and the findings are reported).

Abnormal pregnancy outcomes are considered SAEs. If the outcome of the pregnancy meets the criteria for an SAE (eg, ectopic pregnancy, spontaneous abortion, intrauterine fetal demise, neonatal death, or congenital anomaly in a live-born baby, a terminated fetus, an intrauterine fetal demise, or a neonatal death), the investigator should follow the procedures for reporting SAEs. Additional information about pregnancy outcomes that are reported to Pfizer Safety as SAEs follows:

- Spontaneous abortion including miscarriage and missed abortion;
- Neonatal deaths that occur within 1 month of birth should be reported, without regard to causality, as SAEs. In addition, infant deaths after 1 month should be reported as SAEs when the investigator assesses the infant death as related or possibly related to exposure to the study intervention.

Additional information regarding the EDP may be requested by the sponsor. Further follow-up of birth outcomes will be handled on a case-by-case basis (eg, follow-up on preterm infants to identify developmental delays). In the case of paternal exposure, the investigator will provide the participant with the Pregnant Partner Release of Information Form to deliver to his partner. The investigator must document in the source documents that the participant was given the Pregnant Partner Release of Information Form to provide to his partner.

8.3.5.2. Exposure During Breastfeeding

An exposure during breastfeeding occurs if:

- A female participant is found to be breastfeeding while receiving or after discontinuing study intervention.
- A female is found to be breastfeeding while being exposed or having been exposed to study intervention (eg, environmental exposure). An example of environmental exposure during breastfeeding is a female family member or healthcare provider who reports that she is breastfeeding after having been exposed to the study intervention by ingestion.

The investigator must report exposure during breastfeeding to Pfizer Safety within 24 hours of the investigator's awareness, irrespective of whether an SAE has occurred. The information must be reported using the CT SAE Report Form. When exposure during breastfeeding occurs in the setting of environmental exposure, the exposure information does not pertain to the participant enrolled in the study, so the information is not recorded on a CRF. However, a copy of the completed CT SAE Report Form is maintained in the investigator site file.

An exposure during breastfeeding report is not created when a Pfizer drug specifically approved for use in breastfeeding women (eg, vitamins) is administered in accord with authorized use. However, if the infant experiences an SAE associated with such a drug, the SAE is reported together with the exposure during breastfeeding.

8.3.5.3. Occupational Exposure

The investigator must report any instance of occupational exposure to Pfizer Safety within 24 hours of the investigator's awareness using the CT SAE Report Form regardless of whether there is an associated SAE. Since the information about the occupational exposure does not pertain to a participant enrolled in the study, the information is not recorded on a CRF; however, a copy of the completed CT SAE Report Form must be maintained in the investigator site file.

8.3.6. Cardiovascular and Death Events

Not applicable.

8.3.7. Disease-Related Events and/or Disease-Related Outcomes Not Qualifying as AEs or SAEs

Not applicable.

8.3.8. Adverse Events of Special Interest

Not applicable.

8.3.8.1. Lack of Efficacy

This section is not applicable because efficacy is not expected in the study population.

8.3.9. Medical Device Deficiencies

Not applicable.

8.3.10. Medication Errors

Medication errors may result from the administration or consumption of the study intervention by the wrong participant, or at the wrong time, or at the wrong dosage strength.

Exposures to the study intervention under study may occur in clinical trial settings, such as medication errors.

Safety Event	Recorded on the CRF	Reported on the CT SAE Report Form to Pfizer Safety Within 24 Hours of Awareness
Medication errors	All (regardless of whether associated with an AE)	Only if associated with an SAE

Medication errors include:

- Medication errors involving participant exposure to the study intervention;
- Potential medication errors or uses outside of what is foreseen in the protocol that do or do not involve the study participant.

Such medication errors occurring to a study participant are to be captured on the medication error page of the CRF, which is a specific version of the AE page.

In the event of a medication dosing error, the sponsor should be notified within 24 hours.

Whether or not the medication error is accompanied by an AE, as determined by the investigator, the medication error is recorded on the medication error page of the CRF and, if applicable, any associated AE(s), serious and nonserious, are recorded on the AE page of the CRF.

Medication errors should be reported to Pfizer Safety within 24 hours on a CT SAE Report Form **only when associated with an SAE**.

8.4. Pharmacokinetics

Plasma for analysis of EE and LN

Blood samples of approximately 6 mL ($2 \times 6 = 12$ mL), to provide approximately 2.5 mL plasma for each EE and LN will be collected into appropriately labeled tubes containing K₂EDTA for measurement of plasma concentrations of EE and LN as specified in the SoA. Instructions for the collection and handling of biological samples will be provided in the laboratory manual or by the sponsor. The actual date and time (24-hour clock time) of each sample will be recorded.

The actual times may change, but the number of samples will remain the same. All efforts will be made to obtain the samples at the exact nominal time relative to dosing. Collection of samples up to and including 10 hours after dose administration that are obtained within 10% of the nominal time relative to dosing (eg, within 6 minutes of a 60-minute sample) will not be captured as a protocol deviation, as long as the exact time of the collection is noted on the source document and the CRF. Collection of samples more than 10 hours after dose administration that are obtained ≤ 1 hour away from the nominal time relative to dosing will not be captured as a protocol deviation, as long as the exact time of the collection is noted on the source document and the CRF. This protocol deviation window does not apply to samples to be collected more than 10 hours after dose administration at outpatient/follow-up visits with visit windows.

Samples will be used to evaluate the PK of OC steroids (EE and LN). Samples collected for analyses of OC steroids (EE and LN) concentration may also be used to evaluate safety or efficacy aspects related to concerns arising during or after the study, for metabolite identification and/or evaluation of the bioanalytical method, CCI [REDACTED]

CCI [REDACTED]

Samples collected for measurement of plasma concentrations of OC steroids (EE and LN) will be analyzed using a validated analytical method in compliance with applicable SOPs.

The PK samples must be processed and shipped as indicated in the instructions provided to the investigator site to maintain sample integrity. Any deviations from the PK sample handling procedure (eg, sample collection and processing steps, interim storage or shipping conditions), including any actions taken, must be documented and reported to the sponsor. On a case-by-case basis, the sponsor may make a determination as to whether sample integrity has been compromised.

CCI [REDACTED]

CCI

8.7. Immunogenicity Assessments

Immunogenicity assessments are not included in this study.

8.8. Health Economics

Health economics/medical resource utilization and health economics parameters are not evaluated in this study.

9. STATISTICAL CONSIDERATIONS

Detailed methodology for summary and statistical analyses of the data collected in this study is outlined here and further detailed in an SAP, which will be maintained by the sponsor. The SAP may modify what is outlined in the protocol where appropriate; however, any major modifications of the primary endpoint definitions or their analyses will also be reflected in a protocol amendment.

9.1. Statistical Hypotheses

No formal inferential statistics will be applied to the safety or PK data.

9.2. Analysis Sets

For purposes of analysis, the following analysis sets are defined:

Population	Description
Enrolled	All participants who sign the ICD. A participant will be considered enrolled if the informed consent is not withdrawn prior to participating in any study activity after screening.
Assigned to investigational product	All participants who sign the ICD and meet all eligibility criteria.
Evaluable	All participants enrolled to investigational product and who take at least 1 dose of investigational product.
Safety	All participants enrolled to investigational product and who take at least 1 dose of investigational product.

9.3. Statistical Analyses

The SAP will be developed and finalized before any analyses are performed and will describe the analyses and procedures for accounting for missing, unused, and spurious data. This section is a summary of the planned statistical analyses of the primary and secondary endpoints.

9.3.1. Pharmacokinetic Analyses

The PK concentration population is defined as all participants that received at least 1 dose of investigational product and have at least 1 plasma concentration value reported in at least 1 period. The PK parameter analysis population is defined as all participants that received at least 1 dose of investigational product and have at least 1 of the PK parameters of primary interest reported in at least 1 period.

PK parameters for EE and LN following alone and co-administration with PF-06650833 will be derived from the concentration-time profiles using non-compartmental methods as data permit. The PK parameters to be assessed in this study, their definition, and method of determination are outlined in [Table 2](#). In all cases, actual PK sampling times will be used in the derivation of PK parameters.

Table 2. Plasma Pharmacokinetic Parameter Definitions

Parameter	Definition	Method of Determination
C_{\max}	Maximum plasma concentration during the dosing interval	Observed directly from data
T_{\max}	Time for C_{\max}	Observed directly from data as time of first occurrence
AUC_{last}	Area under the plasma concentration-time profile from time 0 to the time of the last quantifiable concentration (C_{last})	Linear/Log trapezoidal method
AUC_{inf}^a	Area under the plasma concentration-time profile from time 0 extrapolated to infinite time	$AUC_{\text{last}} + (C_{\text{last}}/k_{\text{el}})$, where C_{last} is the predicted plasma concentration at the last quantifiable time point estimated from the log-linear regression analysis
CL/F^a	Apparent clearance	Dose/ AUC_{tau}
PTR	Peak-to-trough ratio	C_{\max}/C_{\min}
$t_{1/2}^a$	Terminal elimination half-life	$\log_2(2)/k_{\text{el}}$, where k_{el} is the terminal phase rate constant calculated by a linear regression of the log-linear concentration-time curve. Only those data points judged to describe the terminal log-linear decline will be used in the regression

a. If data permit

The plasma PK parameters in Table 2 will be summarized descriptively by treatment, as applicable, in accordance with Pfizer data standards. AUC_{last} and C_{\max} for EE and LN individual participant parameters will be plotted by treatment. Plasma concentrations will be listed and summarized descriptively by nominal PK sampling time and treatment. Individual participant and median profiles of the plasma concentration-time data will be plotted by treatment using actual and nominal times respectively. Median profiles will be presented on both linear-linear and log-linear scales.

To assess any effect of PF-06650833 on EE or LN exposures, natural log transformed AUC_{last} and C_{\max} will be analyzed using a mixed effects model with treatment as a fixed effect and participant as a random effect. Estimates of the adjusted mean differences (Test-Reference) and corresponding 90% CIs will be obtained from the model and will be exponentiated to provide estimates of the ratio of adjusted geometric means (Test/Reference) and 90% CIs for the ratios.

The following assessment should be performed:

- Effect of PF-06650833 on OC (EE or LN) exposures with OC alone (Period 1 Day 1 PK) as the Reference treatment and co-administration of PF-06650833 and OC (Period 2 Day 10 PK) as the Test treatment.

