- d. **COVID-19 screening:** COVID-19 screening will be done at screening and Day -1. A subsequent COVID-19 test can be performed if participants admitted for residence develop COVID-19 like symptom(s).
- e. **Vital signs (supine BP, pulse rate):** Vital signs will be collected before dosing.
- f. **COVID-19 questionnaire:** Check exposure to positive participant, residence or travel in area of high incidence and COVID-19 related signs and symptoms.
- g. **COVID-19 testing:** The testing for COVID-19 pathogen by PCR will be performed screening and D-1. A subsequent COVID-19 test can be performed if participants admitted for residence develop COVID-19 like symptom(s).
- h. **COVID-19 check temperature:** To be done twice daily during residence.
- i. **OC dosing:** Participants will be dosed with OC following an overnight fast of at least 10 hours. On the day of co-administration of OC and PF-06650833, the two will be administered simultaneously within 5 minutes.
- j. **PF-06650833 QD dosing:** The daily dose of PF-06650833 will be administered at approximately 08:00 ±2 hours.
- k. **OC PK blood sample:** PK blood samples are to be collected at predose, at 30 minutes and 1, 1.5, 2, 4, 6, 8, 12, 24, 36 and 48 hours post OC dose in Periods 1 and 2.
- l. **OC PK blood sample:** The 24 hour OC PK samples on Period 2 Day 11 must be collected pre PF-06650833 dose.
- m. **Period 2:** There is no washout phase between Period 1 and Period 2.
- n. **Follow-up:** Participants will have a telephone contact at least 28 calendar days, and up to 35 calendar days after the last administration of the investigational product(s). At the discretion of the investigator, telephone contact may be substituted with an on-site visit in case of additional follow-up of open AEs or clinically significant laboratory findings

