4.3. Justification for Dose

The current study will use a PF-06650833 dose of 400 mg MR QD. This is the highest dose of PF-06650833 planned for use in future efficacy and safety trials.

PF-06650833 was well tolerated in doses up to 1000 mg QID for up to 14 days in healthy participants without dose-limiting adverse effects being demonstrated when administered as an orally- administered extemporaneously-prepared IR formulation (Study B7921002).

CCI

CCI

CCI

The dose of combination OC is determined in part by the choice of commercially available products and recent precedents at Pfizer in the conduct of OC DDI studies. PORTIA® (EE and LN) or equivalent containing 30 µg of EE and 150 µg of LN will be used in this study. OC will be administered as a single dose with and without PF-06650833.

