10.8. Appendix 8: Abbreviations

The following is a list of abbreviations that may be used in the protocol.

Abbreviation	Term
→	ongoing/continuous event
β-hCG	a quantitative human chorionic gonadotropin
Abs	absolute
ADL	activities of daily living
AE	adverse event
ALC	absolute lymphocyte count
ALT	alanine aminotransferase
ANC	absolute neutrophil count
ARDS	acute respiratory distress syndrome
AST	aspartate aminotransferase
AUC	area under the concentration-time curve
AUC ₂₄	area under the concentration-time curve from time 0 to 24 hours
AUC _{inf}	area under the plasma concentration-time profile from time 0 extrapolated to infinite time
AUC _{last}	area under the plasma concentration-time profile from time zero to the time of the last quantifiable concentration (C _{last})
AUC _{tau}	area under the plasma concentration-time profile from time 0 to time tau, the dosing interval
AV	atrioventricular
BBS	Biospecimen Banking System
BCRP	breast cancer resistance protein
BID	twice a day
BMI	body mass index
BP	blood pressure
bpm	beats per minute
BUN	blood urea nitrogen
¹⁴ C	a radioactive isotope of carbon
C _{last}	last quantifiable concentration
C _{max}	maximum plasma concentration during the dosing interval
C _{min}	minimum observed concentration
CFR	Code of Federal Regulations
CI	confidence interval
CIA	collagen induced arthritis
CIOMS	Council for International Organizations of Medical Sciences
CK	creatine kinase
CKD-EPI	Chronic Kidney Disease Epidemiology Collaboration
CL/F	apparent clearance
CMV	cytomegalovirus

Abbreviation	Term
CO ₂	carbon dioxide (bicarbonate)
COVID-19	coronavirus disease 2019
CRF	case report form
CRO	contract research organization
CRU	clinical research unit
CSR	clinical study report
CT	clinical trial
CTMS	clinical trial management system
CVw%	within-participant coefficient of variation
CYP	cytochrome P450
DDI	drug-drug interaction
DILI	drug-induced liver injury
DMC	data monitoring committee
CCI	
EBV	Epstein-Barr virus
EC	ethics committee
EC ₅₀	the concentration of a drug that gives half-maximal response
ECC	Emergency Contact Card
ECG	electrocardiogram
eCRF	electronic case report form
EDB	exposure during breastfeeding
EDP	exposure during pregnancy
EE	ethinyl estradiol
EFD	embryo-fetal developmental
eGFR	estimated glomerular filtration rate
EMA	European Medicines Agency
E _{max}	the maximum effect
EU	European Union
EudraCT	European Clinical Trials Database
F	bioavailability
Fa	fraction absorbed
FACS	fluorescent activated cell sorting

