5.3.3. Pharmacokinetic Parameters

Actual PK sampling times will be used in the derivation of PK parameters.

If a PK parameter cannot be derived from a participant's concentration data, the parameter will be coded as NC (ie not calculated). (Note that NC values will not be generated beyond the day that a participant discontinues).

In summary tables, statistics will be calculated by setting NC values to missing; and statistics will be presented for a particular treatment with ≥ 3 evaluable measurements. For statistical analyses (ie, analysis of variance), PK parameters coded as NC will also be set to missing; and analyses will not be performed for a particular parameter if more than 50% of the data are NC.

If an individual participant has a known biased estimate of a PK parameter (due for example to an unexpected event such as vomiting before all the compound is adequately absorbed in the body), this will be footnoted in summary tables and will not be included in the calculation of summary statistics or statistical analyses.

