6. ANALYSES AND SUMMARIES

6.1. Primary Endpoint(s)

6.1.1. Pharmacokinetic Endpoints

The mixed effects model described in [Section 5.2](#) will be applied to AUC and C_{max} . The plasma PK parameters in [Table 2](#) will be summarized descriptively by treatment, as applicable, in accordance with Pfizer data standards. AUC_{last} and C_{max} for EE and LN individual participant parameters will be plotted by treatment. Plasma concentrations will be listed and summarized descriptively by nominal PK sampling time and treatment. Individual participant and median profiles of the plasma concentration-time data will be plotted by treatment using actual and nominal times respectively. Median profiles will be presented on both linear-linear and log-linear scales.

Blood samples for PK analysis of EE and LN will be taken according to the Schedule of Activities given in the protocol.

The following PK parameters (shown in Table 6) will be calculated for EE and LN (if possible) from the concentration-time data using standard noncompartmental methods:

Table 6. Noncompartmental PK Parameters

PK Parameter	Analysis Scale	EE	LN
C_{max}	ln, R	A, D	A, D
T_{max}	R	D	D
AUC_{last}	ln, R	A, D	A, D
AUC_{inf}^*	ln, R	A, D	A, D
CL/F^*	R	D	D
PTR	R	D	D
$t_{1/2}^*$	R	D	D

Key: A=analyzed using statistical model, D=displayed with descriptive statistics, ln=natural-log transformed, R=raw (untransformed), NA=not applicable; *=if data permits, C_{max} = Maximum plasma concentration during the dosing interval; T_{max} =Time for C_{max} ; AUC_{last} =Area under the plasma concentration-time profile from time

zero to the time of the last quantifiable concentration (C_{last}); AUC_{inf} = Area under the plasma concentration-time profile from time zero extrapolated to infinite time, and dose normalized AUC_{inf} ; CL/F = Apparent Clearance; PTR = Peak-to-trough ratio; $t_{1/2}$ = Terminal elimination half life.

Table 7. PK Parameters to be Summarized Descriptively by Treatment

Parameter	Summary Statistics
C_{max} AUC_{last} AUC_{inf}^* CL/F^* PTR	N, arithmetic mean, median, $cv\%$, standard deviation, minimum, maximum, geometric mean and geometric $cv\%$.
T_{max}	N, median, minimum, maximum.
$t_{1/2}^*$	N, arithmetic mean, median, $cv\%$, standard deviation, minimum, maximum.

* If data permit.

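### The only CL/F formula in the plan divides dose by AUCtau, but the contraceptive is given as a single dose and has no dosing interval

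*Protocol*

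**What the plan says.** Protocol Section 9.3.1 says of the EE and LN parameters that "their definition, and method of determination are outlined in" Table 2. The method column of the "Apparent clearance" row reads Dose/AUCtau. AUCtau is not itself a row of that table. Protocol Appendix 8 (Section 10.8) defines it only generically, as "area under the plasma concentration-time profile from time 0 to time tau, the dosing interval", and gives no value for tau.

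On dosing, Protocol Section 4.3 says "OC will be administered as a single dose with and without PF-06650833". The two tablets are taken on Period 1 Day 1 and Period 2 Day 10. Sampling ends with "24, 36 and 48 hours post OC dose in Periods 1 and 2" (Protocol Section 1.3, footnote k).

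The SAP names the parameter in the key to its Table 6 (Section 6.1.1: "Apparent Clearance; PTR = Peak-to-trough ratio") but gives no formula. SAP Tables 6 and 7 make CL/F descriptive on the untransformed scale, conditional on adequate data. Both documents list it as a tertiary/exploratory endpoint.

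**The concern.** Dose/AUCtau estimates apparent clearance at steady state under repeated dosing, where the AUC over one interval equals the single-dose AUC to infinity. Neither EE nor LN is dosed repeatedly here. The only once-daily drug is PF-06650833, which Table 2 does not cover. The formula therefore cannot be carried out as written, and the SAP does not replace it.

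An analyst would have to pick a tau (24 h, or the 48 h end of sampling), use AUCinf without written authority, or leave CL/F uncalculated. A finite tau drops the area beyond tau, so CL/F comes out too high and does not reconcile with the AUCinf in the same summary table. If PF-06650833 speeds elimination, which is the enzyme-induction effect the study was set up to look for, the dropped area is larger in the reference period than in the test period. The rise in CL/F would then look smaller than it is.

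**Working it through.** The plan gives no numerical figure to reproduce, because the issue is a formula.

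**Inputs from the documents.** There is one contraceptive tablet per period. The doses are 12 days apart (3 days of Period 1 plus 9 days to Period 2 Day 10). Samples are nominally at 0, 0.5, 1, 1.5, 2, 4, 6, 8, 12, 24, 36 and 48 h. AUCinf is AUClast plus predicted Clast divided by kel, and AUC uses the linear/log trapezoidal method.

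**Assumptions.** The documents give neither tau nor the half-lives of EE and LN. I used tau = 24 and 48 h and half-lives of 6 to 36 h.

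**Direction.** After a single dose, AUCinf = AUC(0–tau) + AUC(tau–infinity), and the last term is positive for any finite tau. Hence (Dose/AUCtau)/(Dose/AUCinf) = AUCinf/AUCtau > 1. This needs no assumed value.

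**Size.** With mono-exponential decline and k = ln 2 / half-life, the overstatement factor is 1/(1 − exp(−k·tau)). For example, a 12 h half-life with tau = 24 h gives 1/(1 − 1/4) = 1.33.

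**Test/Reference comparison.** If the elimination rate doubles and nothing else changes, the true CL/F ratio is 2. The apparent ratio is 2(1 − exp(−k·tau))/(1 − exp(−2k·tau)) = 2/(1 + exp(−k·tau)). For a 12 h half-life and tau = 24 h this is 2/1.25 = 1.60. If only bioavailability changes (F halves), the truncation factor is the same in both periods and the ratio stays at 2.00.

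| Assumed reference half-life (h) | Overstatement, tau 24 h | Overstatement, tau 48 h | Apparent ratio (true 2), tau 24 h | Apparent ratio (true 2), tau 48 h |
|---|---|---|---|---|
| 6 | 1.07 | 1.004 | 1.88 | 1.99 |
| 12 | 1.33 | 1.07 | 1.60 | 1.88 |
| 18 | 1.66 | 1.19 | 1.43 | 1.73 |
| 24 | 2.00 | 1.33 | 1.33 | 1.60 |
| 36 | 2.70 | 1.66 | 1.23 | 1.43 |

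**Check with absorption, on the protocol's sampling times.** I used a one-compartment oral model with linear-up/log-down AUC. At an assumed absorption rate of 1.5 per h, the overstatement factors in the same half-life order are 1.07, 1.35, 1.69, 2.04 and 2.77 (24 h), and 1.004, 1.07, 1.19, 1.34 and 1.67 (48 h). Varying the absorption rate from 0.75 to 3 per h, the 36 h half-life gives 2.74 to 2.84 (24 h) and 1.67 to 1.69 (48 h).

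**Does AUCinf cure it?** On the same grid, Dose/AUCinf returns the model's true CL/F to within 1% (in model units, 0.0696 against 0.0693 at a 10 h half-life, and 0.0278 against 0.0277 at 25 h). It recovers the true doubling as 2.00 to 2.02 in every elimination-only case.

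**The case against.** The strongest reply is that this is leftover repeat-dose template wording with no effect on inference. Much of that stands. CL/F is exploratory and descriptive. Neither document plans a Test/Reference ratio for it, so the last two columns of the table show what a reader would infer from two descriptive summaries, not a scheduled output. With the same tablet in both periods, a correct CL/F is a constant divided by AUCinf, which the SAP already models. A finite-tau error would also be detectable, because CL/F times AUCinf would not return the dose.

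There are also signs that AUCinf was meant. One footnote in Table 2 makes AUCinf, CL/F and half-life alike conditional on the data, and the SAP Table 6 key describes AUCinf as "extrapolated to infinite time, and dose normalized". These are hints only; neither states a formula, and using AUCinf would still depart from the one that is written.

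Loss of the endpoint is the least likely outcome. SAP Section 5.3.3 sets missing-value coding ("concentration data, the parameter will be coded as NC") for inadequate individual data, not for an unclear formula.

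The half-life formula in the same table looks garbled in the extracted text, so the AUCtau subscript is worth confirming on the source page. A misreading of inf as tau is unlikely. The size is uncertain because tau and half-lives are assumed; the direction is not.

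**Conclusion.** The concern holds. The only stated method for a listed endpoint does not fit a single-dose design, and the SAP does not repair it. For any finite tau, CL/F exceeds Dose/AUCinf. On the closed form, with assumed half-lives of 6 to 36 h, the excess is 7% to 170% at 24 h and 0.4% to 66% at 48 h. On the sampling grid with absorption included, the upper ends become 174% to 184% and 67% to 69%. If AUCinf is used in practice there is no error. The primary Cmax and AUClast analyses and the AUCinf model do not depend on this point. It should be corrected, but it does not put the main result at risk.

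**What to change.** In Protocol Table 2, define CL/F as Dose/AUCinf, keeping the existing data-permitting condition, and state the same formula in SAP Section 6.1.1. In the same edit, make the reference to Table 2 in SAP Section 6.1.1 point to Protocol Table 2, because the SAP's own Table 2 is the study-design table. The other repeat-dose terms in Protocol Table 2 (the dosing interval in the Cmax row, and the peak-to-trough ratio) could be checked at the same time.

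The cost is one formula in each document and one cross-reference; AUCinf is already derived. If the protocol is not otherwise being amended, the SAP line alone would settle the matter. Protocol Section 9 allows the SAP to modify the protocol, and requires an amendment only for major changes to the primary endpoints or their analyses. The one drawback is that CL/F will be missing wherever AUCinf cannot be estimated, which the existing footnote already allows.
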